#### **A. Specific Aims**

We *hypothesize* that neonates delivered preterm and wrapped with a sterile polyethylene wrap while being warmed with a standard neonatal transport warming mattress immediately after birth and awaiting delayed cord clamping will be less likely to be hypothermic at arrival to the neonatal warmer. Since this is not currently a method that is employed, we have insufficient preliminary data to determine a sufficient sample size needed for a randomized controlled trial. **The aim of this grant is to perform a pilot trial investigating the effect size of immediate neonatal warming and wrapping of preterm infants on neonatal temperature.** Our team is well positioned to address these questions as there is tremendous synergy between the maternal fetal medicine and neonatology groups at OU, and our large referral base for preterm deliveries—we accept 600 maternal transfers yearly.

We propose a pragmatic randomized pilot trial evaluating the effect size of this strategy employed for moderate and late preterm infants (32 weeks 0 days to 36 weeks 6 days) who are being delivered by non-emergent cesarean. We plan on enrolling 74 patients and allocating patients to the intervention and control groups 1:1 using a block randomization scheme stratified by gestational age. Patients and clinicians cannot be practically blinded to the interventions given the physical nature of the interventions; however, statisticians will be blinded to the group assignments. Primary outcome will be the difference in temperature of the neonate at time of arrival to the warmer for neonatal evaluation between groups. Secondary outcomes will include temperature at completion of resuscitation, need for NICU admission, temperature upon leaving the delivery room, temperature upon admission to the NICU (if required), hypoglycemia (less than 30mg/dL in the first 24 hours), highest bilirubin level, respiratory support in the form of intubation or continuous positive airway pressure, pulmonary hemorrhage, hyperthermia ( $>37.5$

degrees C), days in the NICU, and composite neonatal morbidity and mortality outcome of death or intraventricular hemorrhage (all grades), sepsis (determined by treating neonatologist). Data obtained from this pilot trial will be used to apply for a NIH K08 grant in order to perform an adequately powered multi-center randomized controlled trial in order to investigate the efficacy of this approach and associated outcomes.

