### **D. Research Design and Methods (What, When, How, Where)**

### Recruitment

The trial will be advertised and introduced to patients admitted to the OU Children's Hospital labor and delivery or antepartum units by research nurses. Interested participants will be consented. We are choosing to only include patients undergoing non-emergent cesarean in order to improve our ability to control parameters such as room temperature and labor-related clinical or subclinical maternal infection, which are known confounders. Further, we are limiting our investigation to fetuses 32-36 weeks gestation, since this population represents the largest preterm delivery population. Recruitment and randomization will be stratified by gestational age with an aim to enroll at least 44 pregnancies at 32- 34 weeks and 6 days and 20 pregnancies between 35- 36 weeks and 6 days. Last, it is impossible to recruit patients outside of the inpatient setting for a study investigating preterm delivery, as such deliveries are rarely predictable in the outpatient setting. There will only be one site for this study, the OU Children's Hospital labor and delivery and antepartum units.

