### Protocol

The proposed study is a pragmatic randomized controlled pilot trial of neonatal warming techniques with participants allocated in a 1:1 ratio using a random block allocation table using blocks of size 4 and 6 that are stratified by gestational age ranges of 35-36 weeks and 6 days and 32-34 weeks and 6 days. Since there cannot be a placebo intervention, neither the patient nor the neonatal team will be blinded to the group assignment. The group assignments will be made and coded by a third party at the time of randomization. Patients will be randomized to their respective groups immediately prior to surgery.

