**E. Chart Review**

All outcomes will be recorded in a REDCap database by research nurses and data managers on the OUHSC campus in prospective fashion. Data will be obtained from maternal and neonatal electronic medical records and only de-identified data will be analyzed from the REDCap database. The primary outcome will be the proportion of hypothermic newborns. Secondary outcomes will include temperature at completion of resuscitation, need for NICU admission, temperature upon leaving the delivery room, temperature upon admission to the NICU (if required), hypoglycemia (less than 30mg/dL in the first 24 hours), highest bilirubin level, maximal respiratory support and duration of respiratory support including but not limited to supplemental oxygen and mechanical ventilation, pulmonary hemorrhage, hyperthermia (>37.5 degrees C), days in the NICU, and composite neonatal morbidity and mortality outcome inclusive of 1) death, 2) intraventricular hemorrhage (all grades), 3) sepsis (determined by treating neonatologist) and 4) Necrotizing enterocolitis. Confounders that will be assessed will include delivery room temperature as reported on the room thermostat, maternal temperature as recorded by anesthesia at the time of delivery, time from delivery to arrival at the neonatal warmer, indication for delivery, indication for cesarean, infant weight, timing of betamethasone administration (time for administration to delivery) and gestational age. Access to the database will be controlled and logged using REDCap's internal systems. Finally, at the completion of the study, the data will be stored for 7 years in order to complete analysis and apply for additional grants prior to being destroyed.

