performed. Informed consent forms will be available in both English and Spanish, and if required hospital translator services will be used to assist in translations during the consent process. A patient's capacity to consent will be determined by her treating physician, if in their opinion they cannot consent to clinically relevant procedures they will not be approached for consent.

Enrollment will be stratified by gestational age with a goal recruitment of at least 44 pregnancies at 32-34 weeks and 6 days gestation and 20 pregnancies between 35-36 weeks gestation.

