#### **J. Statistical Methods**

Since this intervention has not been studied previously and requires cohesion between pediatricians and obstetricians, we will plan on hosting in-person and virtual training for key study personnel. Currently, at OU we deliver approximately 250 neonates between 32 and 36 weeks gestation via cesarean each year. Assuming a 33% rate of enrollment, it would take us approximately 11 months to enroll our target sample size of 74 patients.

Two prior studies, one evaluating epidemiology and the other an intervention, demonstrated that 29% of neonates born in the late preterm period were hypothermic in the delivery room with a standard deviation of 8.8. With the proposed enrollment of 74 preterm infants that meet inclusion criteria, we would have approximately 80% power to detect a difference between the two groups of 20%. Since this intervention has not been evaluated previously and we are using indirect data from other institutions and other interventions, we are assuming a 10% increase in sample size (calculated at 68) to account for variations (total of 74). This is a pilot trial to generate the parameters needed to guide the development of the next-step full-scale multicenter trial. Thus, power calculations for the efficacy of the intervention were completed to ensure we did not need to start with a larger or smaller sample size, given the pilot nature of the project.

For this pilot trial, the baseline characteristics of patients assigned to the intervention and control groups will be estimated and compared as means, medians or proportions, as appropriate for the distribution of the data. Descriptive statistics (i.e., proportions, 95% confidence intervals, means, standard deviation, medians, and interquartile range) will be used to characterize the distribution of the primary and secondary outcome measures among the intervention and control groups. Using an intent-to-treat approach, the primary and secondary outcomes will be compared between treatment groups using Student's t-tests, Wilcoxon rank sum tests, chi-square tests or Fisher's exact tests, as appropriate for the variable distributions.

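### Allocation is stratified by gestational age but the primary comparison is not: the tests stay valid, but SEs and CIs are too wide if the strata differ (minor, free to fix)

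*Combined protocol and SAP*

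**What the plan says.** **Design.** Section D (Protocol) allocates 1:1 from a "random block allocation table using blocks of size 4 and 6 that are stratified by gestational age ranges", the bands being 32 weeks to 34 weeks 6 days and 35 weeks to 36 weeks 6 days. Section A also describes stratified block randomisation, with 74 patients. Section D (Recruitment) states an "aim to enroll at least 44 pregnancies at 32- 34 weeks and 6 days and 20 pregnancies between" 35 weeks and 36 weeks 6 days. Section H repeats the targets: "Enrollment will be stratified by gestational age with a goal recruitment of at least 44 pregnancies" in the lower band, and 20 in the upper.

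**Analysis.** The between-group analysis is one sentence of Section J: under intention to treat, "the primary and secondary outcomes will be compared between treatment groups using Student's t-tests, Wilcoxon rank sum tests, chi-square tests or Fisher's exact tests", chosen by the variable's distribution. No stratum term, stratified test or model is named. The sentence before it lists 95% confidence intervals alongside means, SDs and proportions, as descriptive summaries of the outcomes among the two groups.

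**Confounders.** Section E opens a list with "Confounders that will be assessed will include delivery room temperature" and closes it with gestational age. It does not say how any of them will be assessed.

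**Primary outcome.** Section A has "Primary outcome will be the difference in temperature of the neonate at time of arrival to the warmer for neonatal evaluation between groups". Section E has "The primary outcome will be the proportion of hypothermic newborns". Section A's aim is to "perform a pilot trial investigating the effect size of immediate neonatal warming and wrapping of preterm infants on neonatal temperature".

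**The concern.** Stratified blocking keeps the arms nearly balanced on gestational age, so imbalance in gestational age adds almost nothing to the sampling variation of the treatment difference. A two-sample test that ignores the strata does not take this into account. It leaves the between-stratum spread in its variance estimate and so reports more uncertainty than there is. The design obtains the benefit and the analysis does not credit it.

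What is at stake is the width of the reported interval and some power, in a small pilot whose estimates are meant to inform a larger trial. In addition, naming gestational age as a confounder without a method leaves any adjustment to be chosen once the data are in hand.

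**Working it through.** **Inputs**
- 74 infants, 37 per arm (Sections A and J, 1:1).
- Stratum targets 44 and 20 (Sections D and H). They sum to 64, so 10 of the 74 are unassigned. Scaling gives 74 × 44/64 = 50.9 and 74 × 20/64 = 23.1, so 51/23 is *assumed*. Then p = 23/74 = 0.311 and p(1−p) = 0.214.
- Gap g between strata, in within-stratum SDs: not in the documents. *Assumed* range 0 to 1.0.
- Two-sided 5% level: not stated, *assumed*.
- Effect for power: 0.66 SD, *assumed* because it gives about 80% power at 37 per arm.

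**The plan's own figure.** Section J claims about 80% power with 74 infants for a 20% difference. Read as 29% against 9%, 37 per arm gives 59.5% power, and 80% needs 120 infants. The 74 is recovered only if 29 is treated as a mean: 0.20 × 29 = 5.8, with SD 8.8. That is a separate matter, and this point does not depend on it.

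**Temperature.** With balance inside strata, the sampling variance of the mean difference is σ² × 2/37. The unstratified test estimates it as σ²(1 + g²p(1−p)) × 2/37. The reported SE is therefore too large by the factor R = √(1 + 0.214g²), and type I error is about 2[1 − Φ(1.96R)]. This was checked with 20,000 simulated trials per setting, using blocks of 4 and 6 within strata:

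| Gap g (SD) | R | Type I, formula | Type I, simulated | Power, unadjusted |
|---|---|---|---|---|
| 0 | 1.000 | 5.0% | 5.1% | 80.4% |
| 0.25 | 1.007 | – | 4.7% | 79.3% |
| 0.5 | 1.026 | 4.4% | 4.6% | 78.5% |
| 0.75 | 1.059 | 3.8% | 4.0% | 76.4% |
| 1.0 | 1.102 | 3.1% | 3.2% | 73.9% |

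The stratum-adjusted linear model had type I error of 4.8–5.2% and power of 79.6–80.3% throughout. The adjusted CI half-width is t(71) × √(2/37) = 0.464 SD. Unadjusted, it is 0.476, 0.491 and 0.511 SD at gaps of 0.5, 0.75 and 1.0.

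**The estimate itself.** At those three gaps its sampling SD was 0.232, 0.234 and 0.234 unadjusted, against 0.231, 0.234 and 0.233 adjusted. The mean *reported* SE was 0.238, 0.246 and 0.256 unadjusted, against 0.232 adjusted. Only the reported uncertainty differs.

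**Sensitivity to the split.** A separate simulation with a 50/24 split gave type I error of 4.5% and 3.1%, and power of 78.3% and 73.4%, at gaps of 0.5 and 1.0 SD.

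**Proportion hypothermic.** At 29% overall, total variance is 0.29 × 0.71 = 0.2059, and R = √(0.2059 / (0.2059 − 0.214 × gap²)). For gaps of 10, 20 and 30 points, R = 1.005, 1.021 and 1.050. Simulated type I error was 5.1%, 4.3% and 3.9% for chi-square, and 5.2%, 4.8% and 5.1% for Cochran-Mantel-Haenszel. Power for a 20-point reduction was 60.5% (chi-square) against 60.6% with no gap, and 62.0% against 62.7% with a 10-point gap. In the 50/24 simulation, control rates of 36% and 14% gave 61.5% against 62.6%. Even 40% and 6% gave only 61.7% against 64.8%.

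**Interval for the difference.** None is named, but the planned group means and SDs fix the unadjusted one: difference ± t(72) × √(s₁²/37 + s₂²/37). For 29% against 9% the half-width is 1.96 × √((0.29 × 0.71 + 0.09 × 0.91)/37) = 17 points. Summaries by arm alone do not give the stratum-adjusted interval.

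**The case against.** **It is only an efficiency preference.** Largely true. The tests are valid, the estimate loses nothing, and any error is conservative. A reader might infer that ignoring the strata biases the result or inflates false positives; the working shows neither. The size rests on a gap the documents do not give, and nothing in them supports 0.75–1.0 SD between adjacent bands. What remains is that the sponsor chose gestational age for stratification, and using it in the analysis costs nothing.

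**Section E already contemplates adjustment.** It shows an intention, so it would be wrong to say that gestational age is ignored. But it gives no method and no link to the primary comparison.

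**The missing interval.** A reader might infer that the pilot cannot deliver its effect size because no CI for the difference is promised. The documents do not support that. The group summaries allow the unadjusted interval to be computed, and the planned two-sample tests compare the arms directly, so nothing would be judged by overlap of per-group intervals. A wide interval is a property of any 74-infant trial. Because Section A defines the primary outcome as a difference, Section J's confidence intervals could even be read as covering it, although its wording favours per-group summaries.

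**Limits of the check.** The simulations treat infants as independent. Section F excludes only monochorionic multiples, so dichorionic twins could enter, and that case was not tested. A part of the text directly after the Section J analysis paragraph was removed before review and could not be checked.

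**Conclusion.** The mismatch is real and minor. Allocation is stratified and the named tests are not. If temperature differs between strata by 0.5, 0.75 or 1.0 SD, the reported SE is about 3%, 6% or 10% too large, type I error is about 4.5%, 4% or 3%, and power is about 78%, 76% or 74% instead of 80%. At 0.25 SD the loss is trivial. For the binary outcome the power gain from stratifying is negligible: under 1 point at gaps of 0 and 10 points, and about 3 points in the most extreme case tried. These figures assume the 51/23 split (50/24 for that extreme case), the gaps, a 0.66 SD effect for temperature power, and a two-sided 5% level.

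Stating that the difference will be reported with its CI serves the effect-size aim, but it is a secondary reporting clarification. The point is a free improvement, not a flaw that threatens the trial's conclusions.

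**What to change.** Add to Section J, for the primary outcome: *Arrival temperature will be compared with a linear model containing arm and gestational-age stratum; the adjusted mean difference and its 95% CI will be reported.*

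Sections A and E must first be reconciled on which outcome is primary. If it is the proportion hypothermic: *The proportion hypothermic will be tested with a Cochran-Mantel-Haenszel test stratified by gestational age, without continuity correction; the stratified risk difference and its 95% CI will be reported.* In simulation, a stratified Miettinen-Nurminen interval covered 94.8–95.3%, and a Wald interval was slightly narrow at 93.8–94.1%.

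Secondary outcomes may use the same model where it suits them. Fisher's exact test should stay for rare events.

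The cost is a few lines of text and no new data, since stratum is known at randomisation. If the strata do not differ, power is unchanged: 80.3% adjusted against 80.4% for temperature, and 60.6% against 60.5% for the proportion.

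### Covariates collected as confounders have no stated role in the treatment comparison, and no between-arm difference in degrees C with a confidence interval is pre-specified; one adjusted model may give a more precise estimate at little cost

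*Combined protocol and SAP*

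**What the plan says.** - **Section J, Statistical Methods.** On an intent-to-treat basis, "the primary and secondary outcomes will be compared between treatment groups using" one of four two-sample tests (t, Wilcoxon, chi-square or Fisher), with the choice left to how each variable is distributed. The section also promises descriptive summaries for each arm, including means, standard deviations and 95% confidence intervals, and a comparison of baseline characteristics. In the text supplied this is the only account of the outcome analysis. It contains no regression model, covariate list or stratified analysis, and the gestational-age stratum used for randomisation (Section D) does not reappear.
- **Section E, Chart Review.** "Confounders that will be assessed will include delivery room temperature as reported on the room thermostat", then "maternal temperature as recorded by anesthesia at the time of delivery", and later "infant weight, timing of betamethasone administration (time for administration to delivery) and gestational age". The same list holds "time from delivery to arrival at the neonatal warmer". What assessing these variables means for the analysis is not stated.
- **Section A, Specific Aims.** The aim is to "perform a pilot trial investigating the effect size of immediate neonatal warming and wrapping of preterm infants on neonatal temperature", and the primary outcome is given as a between-group difference in temperature on arrival at the warmer. Section E instead gives the share of newborns who are hypothermic as primary. That conflict is a separate issue.

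**The concern.** The infant has no temperature of its own before the intervention. The nearest substitutes are maternal temperature (where the infant starts), room temperature (what it loses heat to) and weight. The protocol's own background supports their relevance: Section B describes the move from the womb to a cooler room and the role of surface-to-weight ratio, and Section D calls room temperature a known confounder. If these variables do predict arrival temperature, an unadjusted test leaves their contribution in the error term and the interval is wider than it need be. That matters here because the effect estimate is what the pilot is meant to hand to the next trial.

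There is also a pre-specification gap. With no stated use for the listed confounders, an analyst could later choose among them after seeing results. The list includes time to the warmer, which arises after the intervention starts and could be affected by it. Because the test is left to the distribution, the effect measure to be reported between arms is open as well.

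**Working it through.** **1. The plan's own figures.** Section J raises 68 by 10%: 68 x 1.10 = 74.8, taken as 74, so 37 per arm at 1:1. The plan gives no R-squared and no precision target, so there is no stated figure on this point to reproduce. Its 80% power does not reproduce as a comparison of 29% with 9% at two-sided 0.05 (74 infants give 59.5%). That is a separate matter, and 80% serves below only as a reference level.

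**2. Effect of adjustment.** Inputs: N = 74 (Section J); k = 3 covariates (Section E); R² is the share of outcome variance they explain, which is assumed.

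- Variance ratio, adjusted to unadjusted: f = (1 − R²) x (1 + k/(N − k − 3)) = (1 − R²) x (1 + 3/68) = (1 − R²) x 1.044
- Interval width ratio: √f x t(0.975; 69)/t(0.975; 72), where the t ratio is about 1.001
- Equivalent number of infants: 74/f
- Power, if the unadjusted test has 80%: Φ((1.960 + 0.842)/√f − 1.960)

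| R² (assumed) | f | Interval width ratio | Equivalent infants | Power |
|---|---|---|---|---|
| 0 | 1.044 | 1.023 | 71 | 78% |
| 0.05 | 0.992 | 0.997 | 75 | 80% |
| 0.10 | 0.940 | 0.970 | 79 | 82% |
| 0.20 | 0.835 | 0.915 | 89 | 87% |
| 0.30 | 0.731 | 0.856 | 101 | 91% |

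Break-even is where f = 1: R² = 1 − 68/71 = 3/71 = 0.042.

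Simulation with 8,000 trials per setting gave variance ratios of 1.05, 1.00, 0.92, 0.84 and 0.73 for the five rows, in line with the formula.

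**3. With the stratum in the model.** If the reference analysis already contains the gestational-age stratum, the degrees-of-freedom factor goes from 1 + 1/70 = 71/70 to 1 + 4/67 = 71/67. The ratio is 70/67 = 1.045, against 1.044 above, so the table barely moves. R² must then be read as variance explained beyond the stratum.

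**4. The choice between t and Wilcoxon.** Simulating a normality test followed by t or Wilcoxon, at 37 per arm, gave type I error of 4.8% with normal data and 4.9% with skewed data. Power was 80.5%, against 80.7% for always using the t-test. The choice costs almost no precision.

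**The case against.** The strongest reply is that nothing here is invalid. Under randomisation the unadjusted difference is unbiased and its standard error already allows for chance covariate imbalance, so adjustment is an efficiency option, and this is a pilot. That stands.

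Four stronger readings are tempting, and the documents do not support them.

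- **That these are strong predictors.** No correlation or R² appears anywhere. The design also narrows the spread: a room target of 65-70 degrees F (Section D), exclusion of chorioamnionitis (Section F), and 32 to 36 weeks only. Birth weight probably overlaps with gestational age, so the increment beyond the stratum may be small.
- **That the gain is free.** The large-sample factor √(1 − R²) gives 0.949, 0.894 and 0.837 at R² of 0.1, 0.2 and 0.3, suggesting reductions of 5%, 11% and 16%. It ignores the cost of estimating three coefficients from 74 infants.
- **That choosing the test from the data loses precision.** The simulation shows that it does not. It is a question of which effect measure gets reported.
- **That a Wilcoxon result would leave only a p-value.** Section J promises means, standard deviations and intervals by arm, from which a mean difference and its interval can be computed. What is missing is a commitment to report that difference.

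A further limit is that the calculation does not carry over to the binary primary outcome named in Section E.

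What survives is narrower: variables named as confounders are collected, their use is unspecified, and the between-arm estimate is not pinned down.

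**Conclusion.** The point holds as an inexpensive improvement to a valid analysis. The size of the gain depends on an R² that the documents do not give. At 0.10, 0.20 or 0.30 beyond the stratum, the interval for the difference in arrival temperature narrows by about 3%, 8.5% or 14%, worth about 5, 15 or 27 additional infants on a base of 74. Below about 0.04 there is no gain, and the worst case is an interval about 2% wider. The figures assume a continuous outcome, three covariates, 37 independent infants per arm and no missing values. Naming the model and the effect measure in advance is worthwhile even if R² proves low, because it removes later choice among covariates and keeps time to the warmer out of the adjustment.

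**What to change.** Add a paragraph to Section J, settled before the statisticians are unblinded:

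- **Model.** For temperature on arrival at the warmer, fit one linear model with arm, gestational-age stratum, maternal temperature at delivery, room temperature and birth weight.
- **Estimate.** Report the adjusted mean difference in degrees C with a 95% confidence interval from robust standard errors, whatever the distribution. Section F excludes only monochorionic multifetal pregnancies, so cluster by mother if twins are enrolled.
- **Sensitivity analyses.** Report the unadjusted difference with its interval, and the Wilcoxon test.
- **Exclusion.** State that time from delivery to the warmer is not in this model; describe it by arm instead.
- **Planning output.** Report the R² that the covariates add beyond the stratum, for the next trial's sample size.
- **Data handling.** State when the room thermostat is read, which Section E leaves open; a time before delivery is needed. State how a missing covariate is handled, so that no infant drops out of the intent-to-treat comparison.

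The cost is a paragraph of wording, three degrees of freedom beyond the stratum, and possibly a small change to the data collection sheet for the time of the room reading. All the variables are already collected. The choice between the continuous and binary primary outcomes must be settled separately; this model serves the continuous one.

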**I. Risks and Benefits**

This intervention has been previously evaluated at a different time point in the neonatal stabilization process in various studies. A previous study where infants were wrapped from the initiation of resuscitation until admission to the neonatal intensive care unit a 7% risk of hyperthermia with no associated adverse neonatal clinically important consequences. Hyperthermia in this population is defined as temperature >37.5 degrees C. The effect of a combination of warming mattresses and polyethylene wraps is mixed as one study notes a 28% risk of hyperthermia at admission to the NICU in neonates born at less than 31 weeks, while another did not identify any children with hyperthermia. Neither study reported adverse clinical consequences. Perlman and colleagues evaluated 3 observational studies for a total of 8985 patients showing no increase in the risk of hyperthermia. Certainly, we would expect a lower rate of hyperthermia, as the intervention will only be applied until the infant can be brought to the neonatal warmer for a total of 2-3 minutes, contrasted with a longer exposure in the above studies. Of note, none of the above studies have demonstrated an increased risk of adverse clinical outcomes in the setting of iatrogenic hyperthermia. As such, the risk level from the proposed study is likely very low. Similarly, since the study will involve extraction of identifiable data there is an extremely low risk of violating privacy and confidentiality as all staff involved are trained to follow HIPAA and the data will be stored on a secure server.

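### If sparse binary outcomes such as hyperthermia go to Fisher's exact test, 37 per arm makes it markedly conservative; Boschloo's exact test holds the same level with more power at little cost

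*Combined protocol and SAP*

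**What the plan says.** Section J (Statistical Methods) covers all outcomes in one sentence: "the primary and secondary outcomes will be compared between treatment groups using Student's t-tests, Wilcoxon rank sum tests", and then "chi-square tests or Fisher's exact tests, as appropriate for the variable distributions". It states no significance level, no sidedness, no rule for moving from chi-square to Fisher, and no other method for sparse tables. The same section plans proportions with 95% confidence intervals by group and describes the trial as a pilot meant to supply parameters for a larger one.

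The size is "our target sample size of 74 patients", with "participants allocated in a 1:1 ratio using a random block allocation table using blocks of size 4 and 6" in two gestational-age strata, so about 37 infants per arm.

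Hyperthermia is one of the secondary outcomes in section E: "pulmonary hemorrhage, hyperthermia (>37.5 degrees C), days in the NICU". Section I cites earlier work in which wrapped infants had "a 7% risk of hyperthermia with no associated adverse neonatal clinically important consequences", and adds that "one study notes a 28% risk of hyperthermia at admission to the NICU in neonates born at less than 31 weeks". Because exposure here is only a few minutes, the authors state that "we would expect a lower rate of hyperthermia". Hyperthermia at arrival to the warmer is also monitored separately under Interim Analysis of Safety Data, with Lan-DeMets spending after each third of participants.

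**The concern.** Hyperthermia is the neonatal risk that the protocol discusses most, and the protocol expects it to be infrequent. With 74 infants it will probably fall among the outcomes that are conventionally given Fisher's exact test. That test conditions on both margins. With few events only a handful of tables are possible, and the achieved error rate falls well below the nominal one. The unused part of the 5% is lost sensitivity.

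At stake is how a modest excess of overheated infants would be reported and carried into the planning of the multicenter trial. A split of 5 against 0 could appear as a non-significant difference, although another exact test with the same error guarantee would flag it.

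**Working it through.** **Inputs.** From the documents: 74 infants (section J), 1:1 allocation (Protocol), and hyperthermia of 7% in an earlier wrapping study, with a lower rate expected here (section I). Assumed: exactly 37 per arm, a two-sided 5% level, the expected-count-below-5 convention, independent infants, and the event rates used for power. The plan gives no figure for the size of Fisher's test or for power on hyperthermia, so there is no stated value to reproduce on this point.

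**Which outcomes go to Fisher.** With equal arms and *m* events in total, the smaller expected cell count is *m*/2, which is below 5 when *m* < 10. At 7% in both arms, 74 × 0.07 = 5.2 events are expected, or 2.6 per arm.

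**The 5-versus-0 table by Fisher.** Given 5 events, the chance that all fall in one named arm is C(37,5)/C(74,5) = 435,897/16,108,764 = 0.0271. Doubling for the mirror table gives p = 0.054. For 6 versus 0, 2 × 2,324,784/185,250,786 = 0.025. So with no events in the other arm, Fisher needs six.

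**The same table by Boschloo.** The Fisher p-value serves as the test statistic. Boschloo's p-value is the largest probability, over the common event rate π, of a table whose Fisher p-value is no larger than the one observed:

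p = max over π of Σ P(a; 37, π) P(b; 37, π), summed over tables (a, b) with Fisher p ≤ 0.0541.

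Enumerating all 38 × 38 tables gives 0.032. For 7 versus 1, Fisher gives 0.056 and Boschloo 0.032.

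**True type I error.** This is the same sum, taken over each test's rejection region. For Boschloo, the region is every table with Fisher p up to 0.0806, the highest cut-off at which the maximum size stays within 5%.

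| Common rate | Fisher | Boschloo |
|---|---|---|
| Maximum over all rates | 2.9% (near 31%) | 4.7% |
| 7% | 0.75% | 2.1% |
| 5% | 0.31% | 1.2% |

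Boschloo's region contains every table that Fisher rejects, so it cannot be less powerful.

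**Power.** With a zero rate in the control arm, Fisher rejects when X ≥ 6 and Boschloo when X ≥ 5, where X is Binomial(37, p). The row with 2% in the control arm uses the full sum.

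| Assumed rates | Fisher | Boschloo |
|---|---|---|
| 14% vs 0% | 42% | 61% |
| 14% vs 2% | 26% | 39% |
| 10% vs 0% | 16% | 31% |
| 7% vs 0% | 4% | 11% |

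**Interval.** For 5/37 versus 0/37 the risk difference is 13.5 percentage points, with a Newcombe (score-based) 95% interval of 1.4 to 28.0.

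**The case against.** Fisher's test is standard and controls type I error, so nothing in section J is wrong. The convention that sends sparse outcomes to it is not written there, and neither is the 5% level. This stands: the point is about sensitivity and rests on the usual reading. The silence also has a cost. For 5 versus 0, uncorrected chi-square gives p = 0.021, so the result would turn on a choice left open until the data are seen.

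The rates are a fair target too. The 14% and 10% figures are illustrations and appear nowhere in the documents. The 7% comes from infants wrapped for longer, and the protocol expects less. At 7% versus 0%, power is 4% or 11%, so changing the test does not make this trial able to detect the harm it expects. This stands as well.

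The 5-versus-0 contrast is fragile. The blocking does not guarantee 37/37, and 5/36 versus 0/38 gives Fisher p = 0.023. The general conservatism does not depend on that one table. Both tests also assume independent infants, and only monochorionic multiples are excluded, so twins could enter.

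Three stronger readings are tempting and are not supported:

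- **That commoner binary outcomes lose power too.** With 29% versus 9% hypothermic (the plan's 29% less 20 points), about 37 × 0.38 = 14 events are expected. That would normally go to chi-square, with no loss.
- **That the safety monitoring would reach a different conclusion.** Alpha spending lowers the final level. Assuming three equal looks and 5% overall, it is about 0.044 to 0.046 for O'Brien-Fleming-type spending and about 0.022 for Pocock-type. Boschloo's 0.032 passes the first and fails the second, and the type of spending function cannot be read from the text.
- **That infants' safety rests on this p-value.** DSMB review, its ad hoc triggers and the planned confidence intervals do not depend on it.

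**Conclusion.** The point holds as a low-cost improvement in sensitivity, not as an error in the plan. At 37 per arm and an assumed two-sided 5% level, Fisher's test uses at most 2.9% of the permitted 5%, and under 1% at common rates of 7% or less. Boschloo's test keeps the guarantee and adds 13 to 19 percentage points of power at the assumed rates with 10% or 14% in the warmed arm, but only 7 points at 7% versus 0%. At the low hyperthermia rates that section I expects, neither test is adequate, and the risk-difference interval will carry more information than either p-value. The conclusion assumes the conventional expected-count rule, near-equal arms and independent infants. It is confined to sparse binary outcomes in the section J comparisons.

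**What to change.** In section J, before any outcome data are seen:

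1. State the two-sided 5% level for the between-group comparisons.
2. Write down the rule for small expected counts (for example, any expected cell count below 5), and name Boschloo's unconditional exact test in place of Fisher's for those outcomes. Chi-square stays for the rest.
3. Report a 95% confidence interval for the risk difference, score-based or exact unconditional, and give it the main weight when hyperthermia is interpreted.

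The cost is a line or two of SAP wording. No extra infants or data are needed, and standard software provides the test. The one drawback is that readers know Boschloo's test less well than Fisher's. The change should not be presented as altering the outcome of the Lan-DeMets safety monitoring.
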